15.2 Early Study Closure

At any time during the conduct of the trial, if it is the opinion of the investigators that the risks (or benefits) to the patient warrant early closure of the study, this recommendation should be made in writing to the DSMC. Alternatively, the DSMC may initiate suspension or early closure of the study based on its review of the investigator reports.

15.3 Reporting Guidelines

The DSMC has streamlined the reporting process by utilizing reports from OnCore[®]. This has allowed direct view of reports within the Clinical Trials Management System (CTMS); thus discontinuing paper reports. SAE reports are entered into OnCore[®] monthly and reviewed by the DSMC chair and/or coordinator monthly. Findings will be reported to the full DSMC at the time of study review.

15.4 Reporting Death

Death will be reported per local IRB reporting guidelines.

15.5 Study Accrual Oversight

Accrual data will be entered into OnCore[®] system. The Protocol Progress Committee (PPC) reviews study accrual twice per year while the PPC coordinator reviews accrual quarterly.

15.6 Protocol Deviations

Protocol deviations are entered into OnCore[®] and reviewed by the DSMC chair and/or coordinator monthly. Findings will be reported to the full DSMC at the time of study review.

15.7 Unanticipated Problems

Investigators are required to submit unanticipated problems to the DSMC concurrent with their submission of them to the IRB. **Prompt** reporting of unanticipated problems to the IRB is defined as within 5 days for on-site studies.

Unanticipated problems that will be reported **promptly** to the IRB include:

- Major protocol deviation/violation
- Change to the protocol taken without prior IRB review to eliminate apparent immediate hazard to a research subject (e.g. purposeful and for subject safety)
- Complaint of a subject that indicates unexpected risks, or complaint that cannot be resolved by the research team
- Publication in the literature, safety monitoring report, interim result or other finding that indicates an unexpected change to the risks or potential benefits of the research, in terms of severity or frequency
- Change in FDA labeling or withdrawal from marketing of a drug, device, or biologic used in a research study
- Investigator- or sponsor-initiated suspension or hold
- Serious or continuing non-compliance
- Adverse events (see section below)

16 ADVERSE EVENTS

16.1 Definitions of Adverse Events

16.1.1 Adverse Event

An adverse event (AE) is defined as any untoward medical occurrence associated with the use of a drug in humans, whether or not considered drug related. An adverse event can be any unfavorable and unintended sign (e.g. an abnormal laboratory finding), symptom, or disease temporarily associated with the use of a drug, without any judgment about causality. Adverse events will be graded according to the NCI Common Toxicity Criteria, Version 4.0 (**Appendix F**).

16.1.2 Serious Adverse Event (SAE)

A serious adverse event is any untoward medical occurrence resulting in one or more of the following:

- Results in death or ANY death occurring within 28 days of last dose of study drug (even if it is not felt to be drug related)

- Is life-threatening (defined as an event in which the patient was at risk of death at the time of the event; it does not refer to an event which hypothetically might have caused death if it were more severe)
- Requires inpatient hospitalization or prolongation of existing hospitalization

NOTE: Hospitalizations that are not considered SAEs are:

- Hospitalization planned prior to first administration of study drug
- Hospitalization for elective treatment of a pre-existing condition unrelated to the study medication
- Results in persistent or significant disability/incapacity
- Is a congenital anomaly or birth defect
- Is an important medical event (defined as a medical event(s) that may not be immediately life-threatening or result in death or hospitalization but, based upon appropriate medical and scientific judgment, may jeopardize the patient or may require intervention (e.g., medical, surgical) to prevent one of the other serious outcomes listed in the definition above). Examples of such events include, but are not limited to, intensive treatment in an emergency room or at home for allergic bronchospasm; blood dyscrasias or convulsions not resulting in hospitalization; or the development of drug dependency or drug abuse.
- Pregnancy. Pregnancy of a patient or of the female partner of a male patient during the study or within 30 days after the last dose of study drug should be reported via an SAE report. Should pregnancy occur in a female participant during the treatment period, study drug should be discontinued and OnTarget notified immediately. Should a pregnancy occur in a female companion of a male participant during the treatment period, the male participant can continue treatment and OnTarget notified immediately. Any such pregnancy is to be followed until final outcome.

16.1.3 Unexpected Adverse Event

An adverse event not mentioned in the Investigator's Brochure or package insert or the specificity or severity of which is not consistent with the Investigator's brochure or package insert.

16.1.4 Determining Attribution to the Investigational Agent(s)

Attribution: An assessment of the relationship between the AE and the medical intervention. CTCAE does not define an AE as necessarily “*caused by a therapeutic intervention*”. After naming and grading the event, the clinical investigator must assign an attribution to the AE using the following attribution categories:

Relationship	Attribution	Description
Unrelated to investigational agent/intervention	Unrelated	The AE is clearly NOT related
	Unlikely	The AE is doubtfully related
Related to investigational agent/intervention	Possible	The AE may be related
	Probable	The AE is likely related
	Definite	The AE is clearly related

16.2 Adverse Device Effects Definitions

16.2.1 Adverse Device Effect (ADE)

An ADE is defined as any untoward and unintended response to a medical device, in this study, the camera/imaging system. This definition includes any event resulting from insufficiencies or inadequacies in the instructions for use or the deployment of the device, as well as any event that is the result of a user error [ISO 14155-1:2003 (E) 3.1].

All ADEs noted during the study will be reported in the eCRF. Please refer to section 8.3.2.2 for a list of possible ADEs related to the camera/imaging system.

16.2.2 Suspected Adverse Device Effect

A suspected ADE is a subset of all ADEs for which there is a reasonable possibility (i.e., evidence to suggest a causal relationship between the device and the ADE) that the device caused the event. Suspected ADE implies a lesser degree of certainty about causality than adverse device effect.

16.2.3 Unanticipated Adverse Device Effect

An unanticipated ADE is any serious adverse effect on health or safety or any life-threatening problem or death caused by, or associated with, a device, if that effect, problem, or death was not previously identified in nature, severity, or degree of incidence in the investigational plan or application, or any other unanticipated serious problem associated with a device that relates to the rights, safety, or welfare of subjects. [21 CFR 812.3 (s)]

16.3 Adverse Event Reporting Requirements:

Adverse events will be recorded from the time of first study drug administration and for at least 30 days after treatment discontinuation, regardless of whether or not the event(s) are considered related to trial medications. All AEs considered related to trial medication will be followed until resolution, return to baseline, or deemed clinically insignificant, even if this occurs post-trial.

16.3.1 Reporting to the FDA:

Per CFR 312.32 (c), the investigator-sponsor of the investigational new drug (IND) must notify the Food and Drug Administration (FDA) and all participating investigators in a written IND safety report of any adverse experience. There are two types of reports to the FDA: 7-day and 15-day reports.

16.3.1.1 15-Day IND Reports:

The investigator-sponsor of the IND must notify the Food and Drug Administration (FDA) and all participating investigators in a written IND safety report of any adverse experience:

- **associated with use of the drug** that is ***both***
- **serious** ***and***
- **unexpected**

Each written notification shall be made as soon as possible, and no later than **15 calendar** days after the investigator-sponsor's initial receipt of the information.

16.3.1.2 7-Day Reports:

The investigator-sponsor must notify FDA and all participating investigators in a written IND safety report of any adverse experience:

- **fatal or life-threatening experience** that is ***both***
- **associated with use of the drug *and***
- **unexpected**

The FDA will be notified as soon as possible but no later than **7 calendar** days after initial receipt of the information.

Report Content:

Each written notification may be submitted on FDA Form 3500A or in a narrative format and must bear prominent identification of its contents (i.e., "IND Safety Report"). For purposes of this protocol, the **MedWatch Report Form (FDA 3500A mandatory reporting), along with FDA Form 1571, and a cover letter** submitted to the appropriate FDA division, will serve as the written IND safety report. Follow-up information to a safety report should be submitted as soon as the relevant information is available.

Submit:

- MedWatch Report Form (FDA 3500A)
- FDA Form 1571
- Cover Letter

The IUSCC Protocol Development Coordinator should be contacted to assist with all FDA submissions and will be provided with a copy of all events that are reported to the FDA. All IND submissions will be maintained in a master file in the Clinical Research Office of the IU Simon Cancer Center.

16.3.2 Reporting to the IRB:

Unanticipated problems involving risks to subjects or others will be reported **promptly** to the IRB if they:

- unexpected;
- related or possibly related to participation in the research; and
- suggest that the research places subjects or others at a greater risk of harm than was previously known or recognized.

If the serious adverse event does not meet all three (3) criteria listed above, the event does not have to be promptly reported to the IU IRB. However, it should be reported at the time of continuing review.

Prompt reporting of unanticipated problems to the IRB is defined as within 5 days from becoming aware of the event.

16.3.3 Reporting to the IUSCC Data Safety Monitoring Committee:

Regardless of study sponsorship, the study team must enter all initial and follow-up SAE, expedited, and noncompliance reports into OnCore[®] for review by the DSMC chair and/or coordinator. Expedited reports may include IRB Prompt Report Forms, AdEERS reports, MedWatch, and additional SAE forms as required by the sponsor. When follow-up information is received, a follow-up report should also be created in OnCore[®]. This DSMC reporting requirement is in addition to any other regulatory bodies to be notified (i.e. IRB, FDA, pharmaceutical company, etc.). The DSMC chair and/or coordinator will review all SAE, expedited, and noncompliance reports monthly.

16.3.4 Reporting to OnTarget, LLC:

On Target, LLC will be notified of any serious adverse events (SAEs) that occur and are felt to be due to the investigational drug by the investigators. On Target will be notified on the same schedule as IRB reporting (within 5 business days from becoming aware of the event).

Notify [name], COO, On Target Laboratories at [contact] and email: [contact], and [name], Regulatory Consultant, [contact] and email: [contact]

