Secondary Objectives:	
To assess the specificity of tumor fluorescence obtained using OTL38 with folate receptor alpha positive (FRα+) renal cell carcinoma cancer lesions detected via immunohistochemistry
 
To assess the agreement between fluorescence imaging using OTL38 and FRα by immunohistochemistry
 
To assess the agreement between fluorescence imaging using OTL38 and visual/tactile assessments
 
To assess inter-observer variation of tumor fluorescence images captured during surgery, physician rated usefulness of imaging, and safety of OTL38

Study Design:	
This is a pilot, phase 2, non-randomized study in patients with RCC, scheduled to undergo primary, partial, or radical nephrectomy. The current study will have 2 separate arms, but the data from each arm will not be compared with each other.
 
Arm 1: patients with partial nephrectomy for localized RCC
 
Arm 2: patients with radical nephrectomy and lymph node dissection for locally advanced or metastatic RCC

Test Drug/Dose:	OTL38 Injection: folate analog ligand conjugated with an indole cyanine-like green dye as a solution in vials containing 3 mL at 2 mg/mL provided by On Target, LLC. Single-dose 0.025 mg/kg administered IV, less than 2 hours prior to skin incision. Diphenhydramine 25 mg will be given prior to administering the study agent.
Duration of Treatment	
Patients will receive a single dose of OTL38 approximately 2 hours before skin incision.
 
Safety assessments will occur at follow-up phone visit at 10 days (± 3 days) and follow-up office visit at 1 month (± 14 days)

Camera Systems	
The da Vinci[®] Fluorescence Imaging Vision System manufactured by Intuitive Surgical, Inc. or the VSiii 3DHD system manufactured by Visionsense will be used in this study to visualize OTL38-labelled tumors during robotic partial and radical nephrectomies. The SPY Elite Imaging System manufactured by NOVADAQ will be used in open radical nephrectomies. These systems are not approved for use with OTL38, and are therefore considered investigational for purposes of this study.
 
The da Vinci[®] Fluorescence Imaging Vision System has integrated fluorescence imaging capable of providing real-time, imaging identification of fluorescently tagged objects.

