8 STUDY PROCEDURES

8.1 Summary

Administration of the study drug will begin prior to skin incision in the preoperative area where safety monitoring will occur. The tumor resection occurs approximately 2 hours after being brought back to the operating room and so there is no wait time between infusion and being taken back to operating room. Intraoperative fluorescent imaging will be utilized in parallel with the standard operating procedure to capture images during surgery. Images also will be taken of the excised specimen on the back table. The excised specimen will be sent to the pathology department for fluorescent imaging and immunohistochemistry for FR. Subjects will have a 2-5 day hospital stay (normal nephrectomy recovery period) where safety measurements will be taken. Final safety measurements will be taken at the 10-day and 1-month follow-up visits.

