- Concomitant medications: record all postoperative medications (this does not include normal saline or other routine maintenance intravenous fluids)

8.3.3 In-hospital admission (Days 1-5):

- Blood samples: complete blood count w/ differential (CBC w/ diff) and basic metabolic panel (BMP) *on day 1 after surgery*
- Vital signs: recorded per institutional practice
- AE assessment: including hypersensitivity reactions, which could include skin reactions, difficulty breathing, eye or nasal reactions, or gastrointestinal complaints, redness, tenderness, pain, or rash at the injection site or any clinically relevant abnormality (with exception of surgical scars) that was not present at screening.
- ADE assessment: the surgeon will examine the subject to confirm that there are no visible changes to skin (erythema or pigment darkening), tissue or organs related to fluorescence.
- Concomitant medications: record all postoperative medications (this does not include normal saline or other routine maintenance intravenous fluids)

8.3.4 Hospital discharge (Day 2-6):

- Vital signs: recorded per institutional practice
- Review records relating to discharge: date and time that discharge order was written (must occur the same day)
- AE assessment: including hypersensitivity reactions, which could include skin reactions, difficulty breathing, eye or nasal reactions, or gastrointestinal complaints, redness, tenderness, pain, or rash at the injection site or any clinically relevant abnormality (with exception of surgical scars) that was not present at screening.
- ADE assessment: the surgeon will examine the subject to confirm that there are no visible changes to skin (erythema or pigment darkening), tissue or organs related to fluorescence.
- Concomitant medications: record all postoperative medications (this does not include normal saline or other routine maintenance intravenous fluids)

8.3.5 Follow-up phone call (Day 10 [±3 days]):

- AE assessment: including hypersensitivity reactions, which could include skin reactions, difficulty breathing, eye or nasal reactions, or gastrointestinal complaints, redness, tenderness, pain, or rash at the injection site or any clinically relevant abnormality (with exception of surgical scars) that was not present at screening.

- ADE assessment: the surgeon will examine the subject to confirm that there are no visible changes to skin (erythema or pigment darkening), tissue or organs related to fluorescence.

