- Concomitant medications: record any new medications taken since discharge
- A letter will be sent to any subject not contacted after 3 attempts by telephone

8.3.6 Follow-up appointment (1 Month [± 14 days]):

- Physical examination: including weight and vital signs (blood pressures, heart rate, respiratory rate, and temperature). The extent of the physical examination is determined by the investigator (or designee) and is based on clinical relevance to the subject's medical history and scheduled surgical procedure as per standard medical/surgical care.
- Blood samples: complete blood count with differential (CBC w/ diff) and complete metabolic panel (CMP)
- AE assessment: including hypersensitivity reactions, which could include skin reactions, difficulty breathing, eye or nasal reactions, or gastrointestinal complaints, redness, tenderness, pain, or rash at the injection site or any clinically relevant abnormality (with exception of surgical scars) that was not present at screening.
- ADE assessment: the surgeon will examine the subject to confirm that there are no visible changes to skin (erythema or pigment darkening), tissue or organs related to fluorescence.
- Concomitant medications: record any new medications since discharge or follow-up phone call

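### The last scheduled adverse event contact can fall about 14 days before the end of the 30-day recording period that Section 16.3 requires

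*Combined protocol and SAP*

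**What the plan says.** Section 16.3 sets the recording period: "Adverse events will be recorded from the time of first study drug administration and for at least 30 days after treatment discontinuation". It applies whether or not the event is thought related to the drug. The synopsis fixes the start of the clock: "Patients will receive a single dose of OTL38 approximately 2 hours before skin incision". The study calendar (Section 8.2) places that administration on Day 0, so treatment begins and ends on the same day.

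The scheduled contacts after discharge are given in the synopsis as a "follow-up phone visit at 10 days (± 3 days) and follow-up office visit at 1 month (± 14 days"). Sections 8.2, 8.3.5 and 8.3.6 agree; the last is headed "8.3.6 Follow-up appointment (1 Month [± 14 days"). Section 8.1 confirms that these two contacts end the planned safety assessments: "Final safety measurements will be taken at the 10-day and 1-month follow-up visits".

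Two other periods count from the dose. Section 16.1.2 includes in its definition of a serious adverse event (SAE): "Results in death or ANY death occurring within 28 days of last dose of study drug (even if it is not felt to be drug", so attribution does not matter. It also requires an SAE report for a pregnancy, in a patient or a male patient's partner, up to 30 days after the last dose.

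**The concern.** One section sets a minimum of 30 days for collecting events. The visit schedule lets the last planned contact fall well inside that minimum, so a site can keep every visit window and still have no planned occasion to ask about the final part of the period.

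Safety is a secondary objective in both arms (Sections 4 and 12.4), and part of the case for 20 patients in Section 12.3 is the chance of seeing a toxicity. Section 12.8 summarises AEs without naming an observation period. In such a table, a late period in which nobody was asked looks the same as one in which nothing happened. Deaths and pregnancies in the last days of their own windows are in the same position.

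**Working it through.** **The plan's own figure.** Section 12.3 gives an 88% chance of at least one event in 20 patients when the true probability is 0.10. The formula is 1 − (1 − p)^n:

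1 − 0.9^20 = 0.878, or 87.8%. The figure reproduces.

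**Inputs for the date check**
- Dose: Day 0, single (synopsis; Section 8.2).
- Required recording: to at least Day 0 + 30 = Day 30 (Section 16.3).
- Phone call: Day 10 ± 3, so Day 7 to Day 13 (Section 8.3.5).
- Last visit: 1 month ± 14 days (synopsis; Sections 8.2 and 8.3.6).
- Length of 1 month: not defined in days. I assume 30 and show 28 and 31 as the range.

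**Formulas.** Earliest visit = month − 14. Latest visit = month + 14. Days without a planned contact = 30 − earliest visit.

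| Month counted as | Earliest visit | Latest visit | Maximum days of the 30 without a planned contact | Permitted visit days before Day 30 |
|---|---|---|---|---|
| 28 days | Day 14 | Day 42 | 30 − 14 = 16 | 16 of 29 |
| 30 days | Day 16 | Day 44 | 30 − 16 = 14 | 14 of 29 |
| 31 days | Day 17 | Day 45 | 30 − 17 = 13 | 13 of 29 |

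With a 30-day month the maximum gap is 14/30 = 47% of the required period. The phone call does not help, because it is over by Day 13.

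**Deaths and pregnancies.** After a Day 16 visit, 28 − 16 = 12 days of the death window remain (11 to 14 over the range of month lengths), and 30 − 16 = 14 days of the pregnancy window (13 to 16). No contact is scheduled in either.

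**Does another provision fill the gap?** Section 16.3 also follows events to resolution, after the trial if need be, but only those already considered related to the trial medication. That tracks known events; it does not find new ones.

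**Illustration only: could the gap matter for the 88%?** Take the worst case, with all 20 patients last seen on Day 16 and no later event reported.
- If the 10% risk were spread evenly over 30 days (an assumption the documents do not support), the observed risk is 0.10 × 16/30 = 0.053, and 1 − (1 − 0.0533)^20 = 67%.
- If 90% of the risk fell before Day 16, the observed risk is 0.09, and 1 − 0.91^20 = 85%.

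The effect depends almost entirely on when toxicity occurs.

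**The case against.** The strongest reply is that Section 16.3 is a mandatory duty in its own right. Sections 8.2 and 8.3.6 schedule an assessment; they do not say that recording ends there. A reader might infer that a site may stop collecting AEs at Day 16. The documents do not support that: a site that did so would breach Section 16.3. Likewise, the 28- and 30-day periods in Section 16.1.2 define what is reportable, and an early visit does not shorten them. Section 15.4 separately routes deaths through local ethics board reporting.

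A reader might also infer that the 88% in Section 12.3 fails unless everyone is observed for the same length of time. That does not follow. The section states no observation period, and the calculation needs only a 0.10 chance of an observable toxicity per patient.

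The documents also suggest that drug reactions come early. Apart from somnolence, the phase 1a events in Section 5.1.1.2 were suggestive of hypersensitivity, and Section 19.4.7 describes rapid elimination from the circulation. Patients are assessed from administration through surgery, admission and discharge, and again by phone near Day 10. The arms are not compared, so unequal follow-up biases no contrast. Many permitted visit days, Day 30 to Day 44, satisfy both sections.

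All of this stands, and it limits the size of the point. It does not supply the missing contact. Section 16.3 covers every AE regardless of cause, so the early timing expected of drug reactions does not make the rest of its 30 days redundant. A duty to record without an occasion to ask relies on spontaneous reports.

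**Conclusion.** The point holds as an inconsistency between the visit schedule and the recording period. The schedule cannot guarantee the 30-day minimum that Section 16.3 sets. In a patient seen at the early edge of the window, up to about 14 days (13 to 16, depending on how a month is counted) have no planned contact. In that time new AEs, and deaths or pregnancies within their windows, would be known only if someone volunteered them.

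The gap is possible, not certain. How many patients would be seen before Day 30 cannot be told from the documents; it is anywhere from 0 to 20. The practical loss may be small, since the known reactions are mainly of hypersensitivity type. The 88% is arithmetically right and is not shown to be wrong by this point; the 67% and 85% above are illustrations under stated assumptions. The conclusion rests on counting from the single Day 0 dose and on no contact being scheduled after the 1-month visit, both of which the documents state. It is worth correcting because it is cheap to correct, not because it threatens the primary analysis.

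**What to change.** Reconcile the synopsis, Section 8.2 and Section 8.3.6 with Section 16.3, in one of two ways:

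- set the window of the last visit so that it cannot be met before Day 30; or
- keep the window, state that AE, SAE, death and pregnancy recording continues to Day 30, and add a brief telephone or chart check at or after Day 30 for any patient whose visit falls earlier.

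Either way, define 1 month in days. The first option costs wording only, with a narrower choice of visit dates. The second costs wording plus at most one short contact per early-seen patient (20 at the very most), by existing staff. Neither changes treatment or adds a procedure.

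A common Day 0 to Day 30 AE summary in Section 12.8 would make the table easier to read, but it is optional and not needed to remove the inconsistency.
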